### 6.2 Investigational Product Storage

BIOPIN 6 is contained in a sterile pouch which is stored at 4 degrees Celsius.

### 6.3 Investigational Product Accountability

The site principal investigator (PI) or designated study personnel will maintain a log of the receipt of all investigational products and record of dispensing of all investigational products to the subject. Investigational product for each subject will be inventoried and accounted for throughout the trial. Investigational product use during the trial will be recorded on the appropriate drug accountability form.

Unused investigational products will be retained at the clinical site until the end of the study. After final accountability has been performed, unused and explanted used investigational products will be returned to the sponsor.

### 6.4 Investigational Product Administration

BIOPIN 6 is a combination product consisting of naltrexone, poly-d-l Lactic Acid, and polycaprolactone to be implanted subcutaneously.

The justification for implantation, implantation procedures, and implantation risks are summarized in [Appendix A](#).

Data concerning orientation of implants with respect to host physical sites and (for subjects receiving 2 or 3 implants) orientation of the implants with respect to each other will be recorded on case report forms.

## **7. Subject participation**

### **7.1 Recruitment**

Subjects will be recruited from the site's database without regard to ethnicity, race, or socioeconomic level. Standard recruiting practices such as flyers, newspaper advertisements, radio advertisements, or volunteer databases will be used to recruit study volunteers. The site's IRB will approve of all advertisements. Interested candidates between the ages of 18 and 55 years, inclusive, will be pre-screened via a telephone screening process to determine if they are in general good health and available for approximately 5 months.

### **7.2 Informed Consent**

Subjects will be scheduled to meet with the PI or designated investigational staff and receive an explanation of the study purpose and requirements. If still interested after receiving an explanation of the study, the candidate will be given an opportunity to review, inquire about, and sign the study informed consent form approved by the IRB. Subjects will be provided a copy of the signed consent form. After providing informed consent, the subject will proceed to the Screening phase of the study.

### **7.3 Inclusion criteria**

Subjects must meet all of the following criteria to be included in the study:

1. Healthy male or female volunteer, aged 18-to-55 years, inclusive.
2. BMI must be between 18 and 32 kg/m^2 (inclusive) and weigh a minimum of 50 kg (110 lbs).
3. If female, be postmenopausal (at least 2 years prior to dosing) or agree to use an acceptable form of birth control from screening until 12 weeks after dosing. Subjects who claim postmenopausal status will have status confirmed with a follicle-stimulating hormone (FSH) test. Acceptable forms of birth control for females include the following:
  - Vasectomized partner (at least 6 months prior to dosing)
  - Surgical sterilization (bilateral tubal ligation, hysterectomy, bilateral oophorectomy) at least 6 months prior to dosing
  - Non-surgical permanent sterilization (eg, Essure procedure) at least 3 months prior to dosing.
  - Abstinence (must agree to use a double barrier method if they become sexually active during the study)
  - Double barrier (diaphragm with spermicide; condoms with spermicide; Intrauterine device with or without hormones)
  - Oral hormonal contraceptives
4. Not Breast feeding
5. Negative tests for human immunodeficiency virus (HIV), Hepatitis C antibody, Hepatitis B surface antigen, and Covid antigen
6. Able and willing to comply with the requirements of the protocol

7. Able and willing to provide written informed consent
8. Willing to undergo a minor surgical procedure under anesthetic to allow for investigational drug administration in the subcutaneous tissue
9. Agree to avoid blunt trauma to the implantation site
10. Agree that after implantation, not to shower for 2 days and not to bathe/swim for 4 weeks

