**End of study: week 12 (resident, then non-resident)**

Subjects will return for a residential visit on week 12 after dosing. At that time, the implant will be removed and be subject to gross and microscopic descriptions and photos of each tissue capsule. Repeat assessment will be made of adverse effects, EKG, vital signs, clinical chemistry, hematology, concomitant medications, urine drugs, suicidality/depression. To verify diminution

of naltrexone exposure post-implant-removal, blood will be taken for PK pre-explant; 1, 3, 6, 12, 24 hrs after explant (as resident); and 48, 72, and 96 hours after explant (as non-resident).

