Pharmacokinetics (naltrexone and its major metabolite, 6-beta-naltrexol)				
Blood sampling (29 samples)			Predose. Hours 1, 3, 6, 12, 24, 48 and 72. Days 7 and 10. Weeks 2, 3, 4, 5, 6, 7, 8, 9, 10, 11	Week 12: pre-explant and 1, 3, 6, 12, 24 hrs after explant (as resident). 48,72, and 96 hrs (non resident).

 Heart rate (sitting), blood pressure (sitting), respiratory rate, oral temperature

 ALT, albumin, alkaline phosphatase, AST, bilirubin (total and direct), calcium, chloride, cholesterol, creatinine, GGT, glucose, phosphate, potassium, sodium, total protein, uric acid, and blood urea nitrogen (BUN).

 Hemoglobin, hematocrit, red blood cell count (RBC), reticulocytes, white blood cell count (WBC), platelets

 Fibrinogen, prothrombin time (PT), and partial thromboplastin time (PTT).

 Subjects return for a non-residential visit on week 14 for surgical evaluation of explantation site

 For non-resident days, window will be target day [Week 2 (Day 14), Week 3 (Day 21), etc.] +/- 3 days

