### 5.2 Design

Placebo-controlled study of 3 sequential cohorts receiving 4.8, 9.6, or 14.4 g BIOPIN 6 implanted into a subcutaneous pocket in the upper abdominal wall. The placebo will be an implant consisting of the poly-d-l Lactic Acid and polycaprolactone contained in BIOPIN 6 without naltrexone. In each cohort, subjects will be randomized 6 (BIOPIN 6) vs 2 (placebo). At 12 weeks after implantation, the implant will be removed. The safety data for each cohort will be reviewed by the study team before the next cohort is entered into the study.

In accordance with the labelled adverse effects of naltrexone (Vivitrol), entrance criteria are designed to ensure that: subjects are not using opioids, are not using other drugs which in the presence of this opioid-receptor blocker might not be as rewarding as expected, do not have hepatic dysfunction, and do not have suicidal tendencies. After investigational product administration, subjects will be followed for adverse events, hepatotoxicity and reticulocytes in addition to other laboratory measures, suicidality/depression.

Because BIOPIN 6 contains poly-d-l Lactic Acid and polycaprolactone in addition to naltrexone and will be implanted into the subcutaneous tissue, other entrance criteria are not being intolerant of the poly-d-l Lactic Acid and polycaprolactone, not having a bleeding tendency, and not being prone to skin rashes or skin irritation.

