## **7.5 Duration of participation**

Each subject will participate for a maximum of 5 months: up to 1 month of screening, 14 weeks of product administration and follow up.

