## **8.4 Week 12 and 14: study end**

Subjects will return for a residential visit on week 12 after dosing. Prior to removal, the implant **parameters required by Appendix A** will be assessed (distance from incision, photo of site) as

per after-implantation. At that time, the implant will be removed (Appendix B) and be subject to Gross and microscopic descriptions and photos of each tissue capsule. Blood will be taken for PK pre-explant and 1, 3, 6, 12, 24, 48, 72, 96 hrs after explant. Sampling up to 24 hrs will be as residents; sampling at 48, 72, and 96 hrs (+/- 4 hrs) will be as non-residents. Repeat assessment will be made of adverse effects, vital signs, clinical chemistry, hematology, EKG, concomitant medications, urine drugs, suicidality, depression.

On week 14, 2 weeks after implant removal, the subjects will return for a non-residential visit for surgical evaluation of the implant removal site.

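### The contraception commitment ends a fixed 12 weeks after dosing and is not tied to actual implant removal; the main gap is a late-removed or retained implant.

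*Protocol*

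**What the plan says.** Inclusion 3 in Protocol section 7.3 requires women who are not postmenopausal to "agree to use an acceptable form of birth control from screening until 12 weeks after dosing". The accepted methods include oral hormonal contraceptives, barrier methods, sterilization and a vasectomized partner. Intrauterine devices are listed in the double-barrier bullet. Only abstinence has its own time frame: those women "must agree to use a double barrier method if they become sexually active during the study". Section 7.5 describes participation after screening as "14 weeks of product administration and follow up".

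On removal, section 5.2 states: "At 12 weeks after implantation, the implant will be removed". The synopsis then plans blood samples to confirm the decline "of naltrexone exposure post-implant-removal, blood will be taken for PK pre-explant" and at set times afterwards. Section 8.4 adds the late samples: "sampling at 48, 72, and 96 hrs (+/- 4 hrs) will be as non-residents". It also sets the last visit: "On week 14, 2 weeks after implant removal, the subjects will return for a non-residential visit".

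Section 7.6 promises health counseling and medical advice to a subject who discontinues. Section 7.6.2 calls for strong efforts to achieve explantation and, if it is refused, documented contact attempts for adverse events up to 9 months after implantation. Section 10.8.5 covers reporting a pregnancy and following it to term. The timetable in section 2.2 schedules pregnancy tests at screening and day -1 only.

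**The concern.** A contraception requirement normally runs to the end of drug exposure plus a margin. Here the drug source is an implant, so exposure depends on when the implant comes out. Inclusion 3 counts from dosing instead. On schedule, it ends on the explant day with no margin. If removal is late or refused, it ends with the implant still in place.

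Section 4.1 describes the first human use of a product intended for dosing every 6 months, so an implant left in after week 12 may still be releasing drug. The stake is possible fetal exposure in a healthy volunteer. The primary PK analysis and the dose-progression rules are not affected.

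**Working it through.** The plan gives no figure to reproduce here; the check is date arithmetic in days after dosing.

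**Inputs**
- End of commitment (7.3): 12 × 7 = day 84.
- Nominal explant (5.2): 12 × 7 = day 84.
- Last PK sample (8.4): explant + 96 h, window 4 h.
- Intended dosing interval (4.1): 6 months, taken as 26 weeks.
- Contact limit after refused explantation (7.6.2): 9 months, taken as 39 weeks.
- Visit window (2.2, footnote 12): "For non-resident days, window will be target day [Week 2 (Day 14), Week 3 (Day 21), etc.] +/- 3 days". Explant is a residential visit and has no stated window, so applying 3 days to it is an assumption.

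**Late or retained implant**
- Implant in place without a commitment = explant day − 84. With an assumed 3-day delay: 87 − 84 = 3 days.
- Retained, to 6 months: 26 − 12 = 14 weeks (183 − 84 = 99 days).
- Retained, to 9 months: 39 − 12 = 27 weeks (274 − 84 = 190 days).

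**Post-explant sampling that falls after the commitment ends**
- Planned sampling length: 96 / 24 = 4.0 days; with the window, (96 + 4) / 24 = 4.2 days.
- Days beyond the commitment = (explant day − 84) + sampling length.

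| Explant day | Calculation | Days beyond commitment | With 4 h window |
|---|---|---|---|
| 81 (assumed early) | −3 + 4.0 | 1.0 | 1.2 |
| 84 (nominal) | 0 + 4.0 | 4.0 | 4.2 |
| 87 (assumed late) | 3 + 4.0 | 7.0 | 7.2 |

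**Who is affected.** SAP section 4.2 describes two cohorts with 6 active subjects each: 2 × 6 = 12 planned active subjects of both sexes, before replacements. The number of women using oral or barrier methods is not given. Sterilization, a vasectomized partner or an intrauterine device would not lapse at week 12. Abstinent women explanted on schedule are covered if the study is read as running to week 14.

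**Proposed end point.** A visit 14 days after removal, less a 3-day window, is at least 14 − 3 = 11 days after explant, which exceeds 4.2 days. For women explanted on schedule the added commitment is 4 days (96 h sample) to 14 days (week 14 visit).

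**The case against.** The strongest reply is that no harm is shown.

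- **The sampling days are a schedule, not an exposure period.** A reader might infer that women remain exposed for 4 days after removal. The documents do not support that: the samples are there to confirm that levels fall, no post-explant half-life is given, and the nonclinical section is redacted. This objection stands, so the scheduled-explant gap is unquantified.
- **Late removal by 3 days is assumed.** The visit window is written for non-resident days. This stands too; the 7.2 days are illustrative only.
- **Not every woman on a listed method lacks cover.** Intrauterine devices sit under the double-barrier heading but keep working, and premature removal leaves cover until week 12. Both points stand and narrow the group.
- **Withdrawal is already handled.** Counseling, medical advice, efforts to explant, 9-month contact and pregnancy follow-up are all in place. These give routes for the advice, but none mentions contraception, and pregnancy follow-up acts only after the event. This stands in part.
- **Rewording inclusion 3 may help nobody already enrolled.** A reader might infer that the new wording alone closes the gap. It does not: an entry criterion creates no duty for women already in the study and cannot bind someone who has withdrawn. SAP section 3 also says the third dose level will not be opened. This stands, and it is why the advice in 7.6.2 comes first.

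**Conclusion.** The concern holds in a limited form. The commitment ends on a fixed date that coincides with nominal explant, and no visible text ties it to actual removal.

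The main gap is the late-removed or retained implant. If it is retained, contraception ends about 14 weeks before the intended 6 months and about 27 weeks before the 9-month contact limit. The first figure rests on a product aim rather than release data, and the frequency of retention is unknown.

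The secondary gap affects women explanted on schedule who use oral or true barrier methods. Its 4.0 to 4.2 days measure planned sampling; actual exposure is not stated and is probably short.

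The affected women are an unknown subset of 12 planned active subjects. The consent form and the surgical appendices could not be read, so instructions there cannot be ruled out. This is a cheap improvement of minor priority.

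**What to change.** 1. **Section 7.6.2.** Add: *Subjects who are not explanted will be advised to continue contraception through the 9-month contact period.* Raise this at the withdrawal counseling in 7.6 and at each adverse-event contact.
2. **Inclusion 3.** For any further enrolment and later BIOPIN 6 protocols, replace the fixed 12-week end with: *until the week 14 visit, 2 weeks after actual explantation*. The minimum is the 96 h post-explant sample. The sponsor's clinical pharmacologist should confirm the interval.
3. **Consent form.** Align it if it repeats the 12-week limit.

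The cost is about 4 to 14 more days of contraception for women explanted on schedule. Sections 11.5 and 12.3 also mean approval by the sponsor's representative and the IRB, and re-consent of directly affected subjects. No visit, test or sample is added.

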#### **7.4 Exclusion criteria**

Subjects must have none of the exclusion criteria to be included in the study.

1. Clinically significant abnormal finding on the physical exam, medical history, electrocardiogram (EKG), or clinical laboratory results at screening. In particular, values of liver function tests (ALT, AST, bilirubin, albumin, GGT) and kidney function tests (creatinine, blood urea nitrogen) and reticulocytes shall not deviate by more than 25% from the ranges of normal.
2. Blood pressure: systolic >150 mmHg, diastolic >90 mmHg. [Europe Soc Hypertension guidelines]. Repeat measurements up to three times are acceptable.
3. Heart rate: >100 beats/minute.
4. Hemoglobin for female <11.5 and for male <12.5 are excluded.
5. Have a known or suspected history or family history of adverse reactions or hypersensitivity to the study drugs or to drugs with a similar chemical structure.
6. History or presence of gastrointestinal, hepatic or renal disease, or other condition known to interfere with the absorption, distribution, metabolism or excretion of drugs.
7. Is on anticoagulant medications other than aspirin or NSAIDs. Agree to stop aspirin or NSAIDs 1 week prior to Biopin 6 implantation
8. Used any over-the-counter (OTC) medication, nutritional or dietary supplements, herbal preparations, or vitamins within 7 days prior to the first dose of medication.
9. Used any prescription medication (except contraceptive medications and those required for use during the surgical procedure) within 14 days prior to the first dose of study medication.
10. More than moderate drinking averaged over the last month as assessed by history:
  - Moderate drinking is here defined as up to 3 drinks per week. The standard drink will be defined by the guidelines of the National Institute on Alcohol Abuse and Alcoholism (NIAAA) and will contain no more than 14 g of alcohol.
11. Smoking: Use of tobacco or nicotine-containing products within the 3-month period preceding study drug administration is exclusionary.
12. Positive urine drug screen for amphetamines, barbiturates, benzodiazepines, cocaine, opiates, cannabinoids, phencyclidine, propoxyphene, and methadone at the screening and Day -1 tests.
13. Any methadone use 14 days prior to screening, and up to Study Day -1.
14. Has had a naltrexone implant in the past 24 months.

15. Has received treatment with an extended naltrexone product (e.g. Vivitrol) in the past 12 months.
16. Fails the naloxone challenge test (Appendix C)
- 16a. Fails the alcohol breathalyzer test
17. Has a condition which requires treatment with opioid based medication.
18. Has a known hypersensitivity to naltrexone.
19. Has a known hypersensitivity to materials based on poly-d-l Lactic Acid and polycaprolactone (e.g. biodegradable sutures, surgical implants or previous biodegradable implants).
20. Has a known hypersensitivity to local anesthesia.
21. Is prone to skin rashes, irritation or has a skin condition such as recurrent eczema that is likely to impact the implant site area, or as determined by the evaluating physician.
22. Is known to form keloids at the site of skin injury.
23. Demonstrates any abnormal skin tissue in the proposed implantation area
24. Previous surgery to the upper abdominal wall
25. Donated blood or plasma within 30 days prior to the first dose of study medication.
26. Participated in another clinical trial within 30 days prior to the first dose of study medication.
27. Is participating or intending to participate in any other clinical trial during the duration of this study.
28. Any elevated risk for suicide measured using the Columbia Suicide Severity Rating Scale, endorsing any of the items in the past month (C-SSRS, Lifetime)
29. Not as much as “mild” depression as measured by the HAM-D17 test: HAM-D17 score must be 0-10.
30. Any additional condition(s) that in the investigator's opinion would prohibit the participant from completing the study or would not be in the best interest of the participant.

## **7.5 Duration of participation**

Each subject will participate for a maximum of 5 months: up to 1 month of screening, 14 weeks of product administration and follow up.

## **7.6 Withdrawal criteria**

Each subject may withdraw consent at any time during the study without penalty. Counseling about the subject's health will be provided if he/she decides to discontinue participation in the study. Medical advice regarding what is in the best interest of the subject will be provided.

The PI may discontinue the subject's activity without the subject's consent if any of these criteria is met:

- A subject fails to comply with study procedures

- A subject's safety or health may be compromised by further participation
- When premature removal of the implant is needed if pain management requires reversal of naltrexone blockade [10]

### **7.6.1 When and How to Withdraw Subjects**

A subject may end his or her participation in the study at any time. If a subject withdraws, the investigator will make a reasonable effort to determine the reason for the withdrawal from the study and to complete termination procedures as described in section 7.6.2. Telephone calls, registered letters, and email correspondence are considered reasonable efforts for subjects who have missed clinic visits.

A subject may be withdrawn for an AE or serious adverse event (SAE) resulting in a safety concern, or for noncompliance with protocol requirements. When a subject withdraws due to an AE or is withdrawn by the PI due to an AE, the sponsor's representative must be notified within 72 hours. Investigators must follow specific policy regarding the timely reporting of AEs and SAEs to the site's IRB. In all cases, the PI will make a reasonable effort to complete study termination procedures.

### **7.6.2 Data Collected for Withdrawn Subjects**

For subjects leaving the study before the final visit: Ongoing AEs will be followed to resolution or stabilization, if possible. All data collected up to the time of withdrawal will be reported. The subject disposition CRF will be completed, with the reason for withdrawal specified. Strenuous efforts will be made to convince the subject to return to clinic for explantation (including a final clinical chemistry and hematology panel) and for clinical follow-up 2 weeks after explantation. If the subject refuses explantation, documented attempts will be made to contact the subject for AE checks until 9 months after implantation.

### **7.6.3 Replacement of Subjects**

Enrollment will continue until 8 subjects in each group meet the criteria for a study completer. A completed subject is one who provides blood samples through Week 12 that is sufficient for PK parameters to be determined. A "PK completer" is defined as a subject with a maximum of 2 missed PK samples through 24 hrs, a maximum of 1 missed sample from 24 hrs through day 10, and a maximum of 2 missed samples for the 2 week-through- preexplant week 12 time period. If a subject is withdrawn, the replacement subject will be assigned to the same treatment group (BIOPIN implant, placebo implant) as the withdrawn subject.

### **7.7 Entrance of subjects into a cohort**

To verify that a new dose level is initially well-tolerated, approximately half that cohort will complete the 72-hr residential phase surrounding device implantation before the rest of that cohort will have device implantation. In practice, this means that about 4 of the 8 subjects in each cohort will be entered in each of 2 weeks.

## 7.8 Progression of cohorts

7.8.1 Safety considerations: Progression of dose levels (entrance of a new cohort at the next higher dose level) will depend on review of the safety data **at least through week 4** of the prior dose level.

The primary basis on which drug escalation would be limited is based on adverse reactions (an adverse event at least possibly attributable to drug). The committee that evaluates the adverse events for their relationship to drug and implements the progression rules will consist of the PI and a representative of the Sponsor, with the assistance of the Clinical Monitor and the study statistician. Before the blind is broken, the Committee will determine the grade of an AE and whether the AE is not-likely/unlikely related to implantation (ie, there is likely an alternate etiology for the event).

